6.2 Secondary Outcome(s)

- (i) quality of life measured by EQ5D-5L instrument (incorporating pain control) at 30 days and at between 90 and 180 days post-discharge,
- (ii) all-cause mortality at 30 and between 90 and 180 days post-discharge,
- (iii) occurrence of first admission to residential care facility for long-term nursing care at 30 and between 90 and 180 days post-discharge.

The EQ-5D-5L is a self-assessed, health related, quality of life questionnaire which brings the patient (and often their carer) to the fore when attempting to measure the impact of the intervention (see Appendix 1). The scale measures quality of life on a 5-component scale including mobility, selfcare, usual activities, pain/discomfort, and anxiety/depression. It offers the patient the opportunity to express their satisfaction (or not) with the intervention received and is used to determine and quantify the benefits of the intervention.

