A cost-benefit analysis of the physician-delivered STOPP/START intervention RCT of O'Connor et al. indicates that it was not cost-effective (O'Brien et al.); in contrast, the pharmacist-delivered intervention in the parallel RCT by [name] et al. was found to be cost-effective. However, this analysis focused only on in-hospital ADR prevention. The OPTIMATE study proposes to measure cost effectiveness of the DI from the wider public health services perspective, principally the possible benefits derived from avoidance of unscheduled rehospitalization and emergency department attendance. The cost effectiveness analysis will focus on these events, as they are the costliest consequences in financial terms of adverse medication in older multimorbid patients. Quality of life improvement arising from medication optimization interventions is an important theoretical but so far unproven potential benefit for multimorbid older people. This aspect of the DI in OPTIMATE will also be assessed by measurement of quality of life in all randomized patients during post-discharge follow-up period.

From the OPTIMIST trial findings, it is likely that a definitive intervention (DI) most likely to succeed in optimizing medication in hospitalized multi-morbid older people with polypharmacy will be multi-faceted and sustained both during and after the index hospitalization. Furthermore, the DI should incorporate detailed discussion of proposed medication adjustments with the patient, the attending hospital physician, the GP and the community pharmacist in order to maximize its implementation and impact. Additionally, based on well-established published evidence, the DI should be focused on medication optimization at all points of care transition in older people, especially hospital discharge when the risk of inappropriate medication exposure is highest (Cardwell; Weir et al.).

Given the positive results of the OPTIMIST trial arising from an extended pharmacist intervention designed to optimize medication and the positive results of the RCT by O'Connor et al., direct comparison of physician versus pharmacist delivery of the DI is logical. Furthermore, direct comparison between physician- and pharmacist-delivered DI is important since the particular healthcare professional training of the person performing the DI would have an important bearing on

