4.0 Study Procedures and Schedule of Events

The schedule of trial procedures for patient participants in the intervention arm of the trial are shown in Tables 1a and 1b below. To mimic the intervention for blinding purposes of the participants, both control and intervention arm patients will receive a sham intervention in the form of a modified version of the Medication Adherence Rating Scale (MARS; Thompson et al.).

Table 1a: Schedule of events for intervention patients

Timepoints	0/1	2	3	4	5
Study Visit	Baseline (within 72 hours of admission)	Pre-discharge (within 48 hours pre-discharge)	1 Week Follow-up (within 10 days post-discharge)	1 Month Follow-up (within 30 days post-discharge)	6 Month Follow-up (between 90 and 180 days post-discharge)
	Day 1	Day variable	Day 10 (+/- 3 days post-discharge)	Day 30 (+/- 7 days post-discharge)	Between Day 90 and Day 180 post-discharge
Inclusion / Exclusion criteria	X				
Decision-Making Capacity Functional Assessment	X	X**		X**	X**
Informed consent/ proxy assent	X	X**		X**	X**
Patient Demographics	X				
Medical History	X	X		X	X
Medication Reconciliation	X	X		X	X

OPTIMATE Trial

Principal Investigator: [name] [name]

FORTA* criteria	X	X		X	X
Laboratory Results	X	X			
Electrocardiogram review	X				
EQ5D-5L				X	X
Randomization	X				
Medication History (modified SHiM)	X				
Modified Medication Adherence Rating Scale (mMARS)	X				
Barthel Index Score	X	X			
Drug-drug interactions (Stockley's)	X	X		X	X
STOPP/START criteria (PIMs & PPOs*)	X	X		X	X
Face-to-face discussion with senior attending physician or senior resident to highlight potentially inappropriate PIMs and PPOs	X	X			
Face-to-face discussion with patient or nominated proxy (where patient does not have decision-making capacity) to explain details of recommended medication changes.		X			

OPTIMATE Trial

Principal Investigator: [name] [name]

Pre-discharge medication review, documentation of agreed medication adjustments and preparation of report for patient's GP with detailed explanation of recommended medication changes.		X			
Telephone contact with patient's GP to discuss medication changes.			X		
Telephone contact with patient or nominated proxy (where patient does not have decision-making capacity) to define current list of medications, discuss any medication issues and ascertain endpoint information.				X	X
Telephone contact with patient's pharmacist to define medication currently dispensed.			X	X (if necessary)	X (if necessary)

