Telephone contact with patient's GP for endpoint ascertainment (if not available from patient or proxy).				X (if necessary)	X (if necessary)
Unscheduled Readmission Determination				X	X
Unscheduled Emergency Department Attendance Determination				X	X

Admission to residential care facility (long-term)				X	X
All-cause mortality check via registries or if necessary, with the patient's GP.				X	X

Table 1b: Schedule of events for control patients

Timepoints	1	2	3	4	5
Study Visit	Baseline (within 72 hours of admission)	Pre-discharge (within 48 hours pre-discharge)	1 Week Follow-up (within 10 days post-discharge)	1 Month Follow-up (within 30 days post-discharge)	6 Month Follow-up (between 90 and 180 days post-discharge)
	Day 1	Day variable	Day 10 (+/-3 days post-discharge)	Day 30 (+/- 7 days post-discharge)	Between Day 90 and Day 180 post-discharge
Inclusion / Exclusion criteria	X				
Decision-Making Capacity Functional Assessment	X	X**		X**	X**
Informed consent/ proxy assent	X	X **		X**	X**
Patient Demographics	X				
Medical History	X	X		X	X
Medication Reconciliation	X	X		X	X
FORTA* criteria	X	X		X	X

OPTIMATE Trial

Principal Investigator: [name] [name]

Laboratory Results	X	X			
Electrocardiogram review	X				
EQ5D-5L				X	X
Randomization	X				
Modified Medication Adherence rating Scale (mMARS)	X				
Barthel Index	X	X			
Telephone contact with patient or next-of-kin to define current list of medications, discuss any medication issues and ascertain endpoint information.				X	X
Telephone contact with patient's pharmacist to define medication dispensed.			X	X (if necessary)	X (if necessary)
Telephone contact with patient's GP for endpoint ascertainment (if not available from patient or proxy).				X (if necessary)	X (if necessary)
Unscheduled Readmission Determination				X	X
Unscheduled Emergency Department Attendance Determination				X	X

Admission to residential care facility (long-term)				X	X
All-cause Mortality check via registries or if necessary, with the patient's GP.				X	X

* PIMs – Potentially Inappropriate Medications; PPOs – Potentially inappropriate Prescribing Omissions; FORTA Fit fOR The Aged

** If necessary i.e. applies to participants who initially lacked decision-making capacity at the time of their enrolment.

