7.2. Statistical Analysis

Treatment effects for each of the two active intervention arms (versus control) in terms of binary outcomes (e.g. readmission) will be estimated using logistic regression, while Health Related QoL (EQ-5D 5L) will be analyzed using ordinal regression with a logit link function (i.e. a proportional odds model). We will report two models for each outcome: one adjusted for centre and admitting service type; and another further adjusted for age (years), sex, number of comorbidities at baseline, and number of prescribed medications at baseline. Effect estimates will be reported as odds-ratios with 95% confidence intervals and exact p-values. There will be no correction for multiplicity, but we will report results for all outcomes regardless of the result and provide enough information for the reader to make whatever corrections they may consider appropriate. Equivalence tests comparing the two active arms (for each outcome) will be done using a “two one-sided tests” procedure based on a 90% confidence interval (which equates to a 5% type 1 error rate). All analyses will be conducted on an intention-to-treat basis and will be conducted under the quality system and SOPs of the HRB CRF-C Statistics and Data Analysis Unit. A complete statistical analysis plan (SAP) will be pre-registered on the Open Science Framework prior to database lock. Any necessary deviations from this SAP will be documented and explained in the trial report. There will be only one single trial data analysis at the end of the project. All reporting will be carried out in accordance with CONSORT guidelines for clinical trials.

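### EQ-5D-5L is not collected before randomization, so quality of life and QALYs cannot be adjusted for their own baseline, and the baseline Barthel Index is in neither planned model

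*Combined protocol and SAP*

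**What the plan says.** Section 6.2 sets the outcome as "quality of life measured by EQ5D-5L instrument (incorporating pain control) at 30 days and at between 90 and 180 days post-discharge". Section 2.1 agrees, promising "measurement of quality of life in all randomized patients during post-discharge follow-up period". Tables 1a and 1b (Study Procedures and Schedule of Events) tick EQ-5D-5L in the 1-month and 6-month columns only, leaving the baseline, pre-discharge and 1-week columns empty. Section 6.3 on tertiary endpoints draws the QALY from the same follow-up scores.

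The row "Barthel Index Score" in Table 1a, and its counterpart in Table 1b, is ticked at baseline and again before discharge, so all three arms have a baseline functional score.

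Section 7.2 analyses quality of life by "ordinal regression with a logit link function". It reports two models per outcome: one with centre and admitting service type, the other "further adjusted for age (years), sex, number of comorbidities at baseline, and number of prescribed medications at baseline". Neither contains Barthel or any baseline quality-of-life value. A complete SAP is still to be registered before database lock.

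**The concern.** For a repeated score, the patient's own baseline is often the strongest available predictor of the follow-up value, and adjusting for it is a standard way to gain power. Here that value will not exist. Section 2.1 calls improved quality of life an unproven potential benefit and sets out to test it. Sections 2.2 and 3.2 make it a named secondary aim and objective, and the score also feeds the cost-effectiveness work. The only sample-size calculation is for readmission, so any avoidable loss of power falls on an endpoint with no power calculation.

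The two gaps differ in kind. A later SAP can still bring in Barthel. It cannot recover an EQ-5D-5L that was never asked.

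**Working it through.** **Inputs from the documents.** 324 evaluable patients per arm (Section 4.3); the covariates and the proportional odds model (Section 7.2).

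**Inputs assumed, because the documents give none.** Correlation r between baseline and follow-up score of 0.3, 0.5 or 0.7. Share R0 of outcome variance already explained by the planned covariates of 5-10%, or 15-25% if Barthel is added. For the ordinal model, eight equally likely levels and a latent shift of 0.2 SD.

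**1. The plan's own figure.** For 20% versus 12%, two-sided 5%, 80% power: (1.960 + 0.842)² × (0.20×0.80 + 0.12×0.88) / 0.08² = 7.849 × 0.2656 / 0.0064 = 325.7, so 326 per arm. The pooled-variance form gives 329 and the arcsine form 325, against 324 stated. 972 / 0.7 = 1388.6, so 1389, or 463 per arm. The figure reproduces and is not in question here.

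**2. The schedule.** Section 6.2, Section 2.1, Table 1a and Table 1b all place EQ-5D-5L after discharge. No section places it earlier. The absence is consistent across the document and is not a slip in one table.

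**3. QALY, linear scale.** With full overlap between what the covariates and the baseline score explain, the further share of variance removed is 1 − (1 − max(r², R0)) / (1 − R0). Full overlap gives the smallest net gain for a given r; less overlap would give more.

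| R0 | r = 0.3 (r² = 9%) | r = 0.5 (r² = 25%) | r = 0.7 (r² = 49%) |
|---|---|---|---|
| 5% | 1 − 0.91/0.95 = 4.2% | 1 − 0.75/0.95 = 21.1% | 1 − 0.51/0.95 = 46.3% |
| 10% | 1 − 0.90/0.90 = 0% | 1 − 0.75/0.90 = 16.7% | 1 − 0.51/0.90 = 43.3% |
| 15% (with Barthel) | 0% | 1 − 0.75/0.85 = 11.8% | 1 − 0.51/0.85 = 40.0% |
| 25% (with Barthel) | 0% | 1 − 0.75/0.75 = 0% | 1 − 0.51/0.75 = 32.0% |

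The last two rows show that a useful Barthel score would recover part of what the missing EQ-5D-5L costs.

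**4. Quality of life, proportional odds.** The equivalent sample-size factor is the squared ratio of the mean z statistic with and without the baseline score. Simulation at 324 per arm (500 runs), net of covariates explaining 5-10% and with full overlap, gives 1.00-1.04 / 1.16-1.27 / about 1.78. The linear analogue, (1 − R0) / (1 − max(r², R0)), serves as a check: 0.90/0.90 to 0.95/0.91 = 1.00-1.04; 0.90/0.75 to 0.95/0.75 = 1.20-1.27; 0.90/0.51 to 0.95/0.51 = 1.76-1.86. The two agree within simulation noise. With R0 at 25% the simulated factor is 1.00 / 1.00 / about 1.46 (linear at r = 0.7: 0.75/0.51 = 1.47).

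**5. Form of the gain.** In this model adjustment moves the odds ratio away from 1 and slightly raises its standard error. Against a model without covariates the rise is 0.5% / 1.4% / 3.7% with eight levels, and about 0.9% / 2.6% / 6.5% with five. The gain is in power to detect a difference; the interval on the odds-ratio scale does not narrow.

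**The case against.** The strongest reply is that the omission was a reasonable choice. The instrument asks about health on the day (Appendix 1), and the baseline visit falls within 72 hours of an acute admission. Some patients enter by proxy. A score taken then may say little about health one to six months after discharge. At r = 0.3 the net gain is 0-4%, and nil if Barthel raises the explained share to 15% or more. The planned covariates are sensible, and only readmission is powered. All of this stands: the loss may be close to nil, and the plan does not contradict itself. It does not explain why a functional score collected in every arm is left out of the quality-of-life model.

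The ordinal figures also depend on a level count with no source. Appendix 1 has five levels per dimension and a 0-100 scale, and Section 7.2 does not say which score is modelled. This stands too, so those figures are illustrative.

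A reader might infer that Barthel should enter the logistic models for readmission and ED attendance as well. The figures do not make that case. For 20% versus 12% at 324 per arm, with an assumed covariate log odds ratio of 0.3 to 0.8 per SD, the superiority gain is worth 1-8% in sample size. At 20% in both active arms the 90% interval used for the equivalence tests ("based on a 90% confidence interval (which equates to a 5% type 1 error rate") widens by 1-5%. Physician-pharmacist equivalence is Hypothesis 2, so this is a trade-off and leaving Barthel out there is not an omission to correct.

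A reader might also infer that a baseline EQ-5D-5L would supply the starting utility for the QALY. It would not: follow-up is counted from discharge, and an admission score is not the discharge value. The QALY calculation is not yet specified, so that question is separate.

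**Conclusion.** The point holds as a modest one. EQ-5D-5L has no pre-randomization value, so neither quality of life nor the QALY can be adjusted for it, and baseline Barthel is in neither model. At r = 0.3 / 0.5 / 0.7 the net cost is at least 0-4% / 17-21% / 43-46% of QALY variance. For quality of life it is equivalent to about 0-4% / 16-27% / 78% in sample size. These figures rest on assumed correlations, a 5-10% covariate share, full overlap and, for quality of life, eight levels and a 0.2 SD shift.

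Two stronger readings are tempting. The first is that the missing baseline biases the comparison. Randomization rules out systematic bias, and chance imbalance in baseline health is the same loss of power seen from another side. The second is to take the ordinal sample-size factors of 1.10 / 1.34 / 1.90 as the loss. Those compare baseline adjustment with a model that has no covariates, and Section 7.2 does not plan such a model. The primary endpoints do not depend on EQ-5D-5L at all.

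**What to change.** **1. Baseline EQ-5D-5L.** For any patients still to be enrolled, add it (self or proxy, with the respondent recorded) at the existing baseline visit before randomization, and adjust quality of life and the QALY for it. Earlier patients can enter with a constant plus a missing-value indicator, since the gap depends on enrolment date and not on arm. With a fraction f covered, the gain shrinks roughly in proportion: at r = 0.5 and f = 0.5, 0.5 × 16.7-21.1% = about 8-11% of QALY variance. The Synopsis gives an end date of 15/07/2024; if no patients remain to be enrolled, report the missing baseline as a limitation.

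**2. Baseline Barthel.** In the SAP still to be registered, pre-specify the baseline value, not the pre-discharge one, in the further-adjusted model for quality of life and in the QALY analysis. Instruct researchers to score it before requesting allocation: the tables do not state the order within the visit, and Section 4.3 has allocation revealed at once. For patients already enrolled the order may not be verifiable, so keep the first model, without Barthel, as the check.

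**Cost.** A few minutes' questionnaire for acutely ill patients, mixed self and proxy answers, and partial coverage; then SAP wording and one instruction to researchers. The adjusted quality-of-life odds ratio becomes conditional on more covariates, with a slightly larger standard error. No new visit is needed.

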Intervention: The definitive multi-faceted intervention will consist of the following components: (i) modified structured history of medication (mSHiM), (ii) Screening Tool of Older Persons' Prescriptions (STOPP) and Screening Tool to Alert to Right Treatment (START) screening for PIMs and PPOs using STOPP/START version 3, (iii) drug-drug interactions screening, using Stockley's Drug Interaction Checker (iv) face-to-face consultation with attending hospital physicians to discuss PIMs, PPOs, interactions and other issues, (v) pre-discharge medication review and adjustment, (vi) detailed medication adjustment discharge report to patients' general practitioners (GPs), (vii) follow-up contact with patients' GPs and community pharmacists at 1 week and 1 and 6 months post-discharge.

Patients in the control arm (standard pharmaceutical care) will receive a sham intervention i.e. modified Medication Adherence Rating Scale (MARS) questionnaire.

Outcome measures: Primary endpoints will include: (i) unscheduled readmission within 30 days post-discharge, (ii) unscheduled readmission within between 90 and 180 days post-discharge, and (iii) ED attendance within 30 days and between 90 and 180 days post-discharge. A primary composite endpoint of unscheduled readmission or ED attendance within 30 days and between 90 and 180 days post-discharge will also be ascertained. Secondary endpoints are: (i) quality of life measured by EQ5D-5L instrument (incorporating pain control) at 30 days and at between 90 and 180 days post-discharge, (ii) all-cause mortality at 30 days and at between 90 and 180 days post-discharge, (iii) first admission to residential care facility for long-term nursing care at 30 days and at between 90 and 180 days post-discharge. Treatment effects for each of the two active intervention arms (versus control) will be estimated and equivalence tests comparing the two active arms (for each outcome) will be undertaken to determine the effectiveness of the DI as delivered by a physician compared to a pharmacist.

An economic evaluation of the DI as delivered by a trained physician and by a trained pharmacist will also be undertaken, involving

- Quality Life Adjusted Year (QALY),
- cost per hospital readmission avoided, and
- cost per ED attendance avoided.

Time frame: 36 months from project start to final report submission.

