Within 72 hours of admission, patients who are potentially suitable for trial enrolment will be approached by the primary researchers (PRs) and informed about OPTIMATE in outline. If they meet inclusion criteria and do not have exclusion criteria, they will be asked to provide informed consent to trial enrolment. Recommended best practice for assessment of decision-making capacity of older patients who may be suitable for the OPTIMATE trial, involves formal assessment of capacity. Where necessary, the patient's mental capacity will be evaluated using the **OPTIMATE Decision-Making Capacity Functional Assessment** guidelines document in the OPTIMATE Manual of Operations. The patient will then be randomized to either the control arm (usual pharmaceutical care), pharmacist-delivered DI arm or physician-delivered DI arm of the trial. Randomization will proceed in a 1:1:1 ratio. The randomization process will be performed electronically using Castor EDC's block randomization algorithm. Patient enrolment will be sequential. With individual level randomization, there is the theoretical risk of control group contamination. This is where both control and intervention patients could be under the care of the same physician, thereby presenting a risk of medication advice learnings in intervention patients being applied unwittingly to control patients. However, in practice, as was seen in the pre-SENATOR observation study (Lavan et al.), variation in reported incidence of ADRs across various medical and surgical specialties in the 6 multi-national participating clinical sites was so large that meaningful cluster randomization was considered both impractical and unnecessary. Furthermore, in the SENATOR trial itself ([name] et al.), although uptake of medication optimization advice was generally poor, there was no evidence of contamination of the control population.

Randomization will be stratified by study site and by admitting service type (i.e. medical vs. surgical). The stratum-specific randomization lists will be generated electronically within Castor EDC, using a validated variable block randomization model. Once a patient has given consent and been enrolled onto the study, their data will be irreversibly added to the study database. From this point, the

primary researchers will receive randomization outcomes immediately upon activating the randomization request on the electronic Case Report Form (eCRF) within the Castor EDC.

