6.0 Outcome measures

6.1 Primary Outcome

- (i) unscheduled readmission within 30 days post-discharge,
- (ii) unscheduled readmission between 90 and 180 days post-discharge, and
- (iii) ED attendance within 30 and between 90 and 180 days post-discharge.

A primary composite endpoint of unscheduled readmission or ED attendance within 30 and between 90 and 180 days post-discharge will also be ascertained.

Treatment effects for each of the two intervention arms versus the control arm will be estimated for each outcome. Equivalence tests comparing the two active arms (for each outcome) will be done to compare DI delivery by physician with DI delivery by pharmacist.

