11.0 Potential Risks of the intervention and the study procedures: (if applicable)

11.1 Adverse Event reporting (if applicable)

Adverse clinical events are expected to occur with a substantially high frequency in the patient population participating in OPTIMATE, given their age, comorbidity and frailty profile.

The definitive intervention (DI) to be deployed in OPTIMATE is considered intrinsically low risk, given that all of the advice points to be offered to patients' attending hospital medical staff and GPs are evidence-based and may be accepted or rejected by the patients' hospital doctors or GPs as they see fit.

Nevertheless, errors may possibly occur if primary researchers use patients' data incorrectly when applying STOPP/START criteria or Stockley's drug interaction software in the detection of drug-drug and drug-disease interactions.

Any actual or suspected significant adverse events experienced by patients arising out of application of the DI will be reported by the primary researcher to the following personnel within 24 hours of detection:

- (i) The trial PI.
- (ii) The local trial co-PI where the adverse event has been detected.
- (iii) The independent trial monitor.

The PI will co-ordinate an online discussion of the suspected adverse event within 48 hours of receiving notice of the event with the local trial PI, the primary researcher who has reported the adverse event and the independent trial monitor. If there is consensus that a clinically significant adverse clinical event arising out of applying the intervention has occurred, the adverse event will be reported to the TSC. The TSC chairperson will convene a meeting of the TSC within one week of notification to examine the details of reported potential adverse event and report back to the TMG within 24 hours of its deliberations.

Any adverse event deemed potentially attributable to incorrect/erroneous application of the DI, in the judgement of the local trial co-PI, will be investigated fully by the independent trial monitor within 2 weeks of the adverse event report.

An electronic record of all reported adverse events possibly relating to the application of the DI will be kept securely at the UCC Clinical Research Facility as part of the OPTIMATE trial record for further scrutiny/examination.

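### Deaths between randomization and discharge are not counted in the mortality outcome and have no defined value in the readmission and ED analyses

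*Combined protocol and SAP*

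**What the plan says.** Section 4.3 places enrolment early in the index admission: "Within 72 hours of admission, patients who are potentially suitable for trial enrolment will be approached". After consent, "The patient will then be randomized to either the control arm (usual pharmaceutical care), pharmacist-delivered DI arm or physician-delivered DI arm of the trial". The intervention also begins in hospital. The synopsis lists "face-to-face consultation with attending hospital physicians to discuss PIMs, PPOs, interactions and other issues", and Table 1a marks STOPP/START screening, interaction screening and that discussion at baseline and again before discharge.

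The outcomes run on a different clock. Section 6.1 states: "A primary composite endpoint of unscheduled readmission or ED attendance within 30 and between 90 and 180 days post-discharge will also be ascertained". In section 6.2, mortality is "all-cause mortality at 30 and between 90 and 180 days post-discharge" and quality of life is measured "at 30 days and at between 90 and 180 days post-discharge"; residential care admission has the same timing. Tables 1a and 1b mark the mortality check only at the 1-month and 6-month visits.

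Section 7.2 says "All analyses will be conducted on an intention-to-treat basis". It gives no rule for a patient who dies before discharge, and it defers a complete SAP to registration before database lock. Section 12.0 deals with withdrawal, not death. Reporting under section 11.1 concerns "Any actual or suspected significant adverse events experienced by patients arising out of application of the DI".

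**The concern.** Being discharged alive is an event after randomization. An outcome whose clock starts at discharge is defined only for patients who reach it, so the groups compared need not be the groups that were randomized. For readmission and ED attendance this start point is natural, but the plan must still say what happens to patients who never reach it. For all-cause mortality there is no such reason to start at discharge. The chosen start omits the inpatient period in which the first medication recommendations are made, when an effect on survival in either direction could first appear.

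If in-hospital mortality were the same in all arms, the loss would be mainly of information. If it differed, the post-discharge comparisons could be biased and the mortality comparison would miss part of the difference.

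**Working it through.** **The plan's own figure.** Section 4.3 gives 20% against 12%, two-sided 5%, 80% power and 324 per arm. With unpooled variance, n = (1.960 + 0.842)² × (0.20×0.80 + 0.12×0.88) / 0.08² = 7.849 × 0.2656 / 0.0064, or 326 per arm. With pooled variance it is 329. Power at 324 is 79.5%, so the figure reproduces closely. Then 972 / 0.7 = 1389, or 463 per arm. The arithmetic is not in dispute.

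**Following one patient.** Take a patient randomized on day 2 who dies in hospital on day 8. There is no discharge date.
- Mortality (6.2): the intervals start at discharge, so the death falls in none of them.
- Readmission, ED attendance and composite (6.1): no value is defined. The logistic model either omits the patient or enters a zero, which scores an in-hospital death as a success.
- Quality of life and residential care (6.2): same clock, and no rule for death.
- FORTA (safety outcomes): scored at baseline and discharge as well as later, but it rates drug appropriateness and does not record death.

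**How many patients.** The documents give no in-hospital death rate, so these rates are assumptions.

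| Assumed rate | Of 1389 | Per arm of 463 |
|---|---|---|
| 2% | 28 | 9.3 |
| 4% | 56 | 18.5 |
| 8% | 111 | 37.0 |

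**Whether direction can change.** Assume in-hospital mortality of 6% in control and 4% with the intervention, and 20% readmission among control survivors. Assume no intervention effect on readmission in the 94% who would survive under either arm, and 50% readmission in the 2% who survive only with the intervention.
- Dropped: control 20.0%; intervention (0.94×0.20 + 0.02×0.50) / 0.96 = 0.198 / 0.96 = 20.6%. Favours control.
- Scored event-free: control 0.94×0.20 = 18.8%; intervention 19.8%. Favours control.
- Death or readmission in all randomized: control 0.06 + 0.188 = 24.8%; intervention 0.04 + 0.198 = 23.8%. Favours the intervention.

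The shifts are small, about 0.6 to 1 point, but the sign depends on a rule that the plan does not state.

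**Effect on power.** If in-hospital deaths lie within the 30% attrition allowance, 324 per arm stands. If they come on top, the evaluable number is 463 × (1 − m) × 0.7, where m is the in-hospital death rate. At 2%, 4% and 8% this gives 318, 311 and 298 per arm, with power of 78.7%, 77.8% and 76.1%.

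Counting in-hospital death as an event, with equal rates in both arms and 324 analysed per arm, changes the contrast. At 4% it becomes 0.04 + 0.96×0.20 = 23.2% against 0.04 + 0.96×0.12 = 15.5%. Power is 74.5%, 69.7% and 60.9% at the three rates. That supports using it as a sensitivity analysis and not as the primary one.

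**The case against.** A reader might infer that the intention-to-treat analysis is not delivered. The documents do not support that. No section restricts an analysis to patients discharged alive, and the full SAP, where denominators and deaths would normally be settled, is still to be registered. What stands is that the stated clock and the stated principle conflict until a rule is written.

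A reader might also infer that these deaths are absent from every outcome and invisible everywhere. That too goes too far:
- FORTA is scored before discharge.
- The economic analysis (section 6.3, tertiary endpoints) takes in readmissions and ED attendances for everyone randomized, which allows a zero-event reading.
- The steering committee takes on data-monitoring roles that include safety data (section 9.0), so attribution to the intervention is not the only safety route.
- CONSORT reporting may show the deaths in the participant flow.
- Mortality at 30 days after discharge could be read as cumulative vital status, though the text does not say so.

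None of these is a planned comparison of in-hospital deaths by arm.

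On size, excluding terminal illness, ICU admission and palliative, oncology and haematology admissions argues against the upper assumed rate. Nor would counting these deaths make a modest difference easy to detect: with 463 per arm, power for 2% against 4% is about 43%, for 4% against 6% about 29%, and for 8% against 10% about 18%. The case for counting them is an unbiased estimate, not a powered test.

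It would also be wrong to assume that the change needs wording only. The documents name a mortality check and survival at follow-up, but not a date of death. The last check may also fall anywhere from day 90 to day 180.

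**Conclusion.** The concern holds for the primary and secondary endpoints. As section 6.2 is written, deaths between randomization and discharge fall outside the mortality outcome, and section 7.2 gives them no value in the readmission and ED models. The number affected cannot be derived from the documents. The 28, 56 and 111 rest on assumed rates, and the reversal of direction is an illustration of what could happen, not a forecast. The sample size calculation is not faulted, and discharge remains a reasonable start for readmission and ED attendance. The point should be settled before the SAP is registered.

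**What to change.** In sections 6.2 and 7.2, and in the SAP to be registered:
1. Count all-cause mortality from randomization in all randomized patients, in-hospital deaths included. Do this either cumulatively to each scheduled check or as time to death censored at the last vital-status check. The second copes better with unequal length of stay and the wide window for the last check.
2. Keep discharge as the start for readmission and ED attendance, and state how a death before discharge enters those models.
3. Report by arm the numbers randomized, died in hospital and discharged.
4. Add one sensitivity analysis of the composite in all randomized patients with in-hospital death counted as an event.

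Cost: wording in two sections, one table and one analysis. Date of death must be confirmed as a data item. If status at a fixed 180 days is wanted, the last registry check must be timed to cover that point, which is a small procedural change.
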